- c. *EGFR* gene (FISH analysis): EGFR, HER-1 (7p11)/SE7 probe (Cat# KI-10702, Kreatech, Durham, NC).

For copy number analysis of *EGFR*, *MET* and *HER2*, two 5um sections mounted on charged slides will be used for each FISH assay (a total of 6 slides pre-treatment and 6 slides from the re-biopsy at progression). The ratio of specific gene signals to centromeric probe signals will be used to calculate copy number. For all three genes, a ratio >2.0 is interpreted as amplification of the gene if at least 50 nuclei are counted based on current literature. (18, 19, 20, 21)

[name] is the key contact for questions regarding this translational medicine study:

[name]
Department of Pathology
Yale University School of Medicine
[name]
[name]
Email: [contact]

Statistical Design:

1. To evaluate the prognostic role of these molecular alterations (e.g. *MET*, *EGFR* or *HER2* amplification) for *resistance* to afatinib plus cetuximab or afatinib alone.

For each potential marker, a logrank test at the 5% level will be used to compare OS and PFS between patients with amplification versus patients without amplification. The following table details the power to detect a two-fold difference in median PFS using a 2-sided 0.10 level logrank test across a range of possible marker prevalence.

Marker prevalence	Power
5%	73%
10%	93%
15%	98%
20%	99%

HER2 amplification is expected to be seen in approximately 1% and *MET* amplification in 3% of patient specimens at baseline. The relationship between OS, PFS and these abnormalities will be evaluated as above, although the power to detect differences is expected to be low.

Further comparisons will be performed within treatment arms. To assess a differential effect by treatment arm, Cox regression will be used to test treatment interaction, again using OS and PFS as the outcome.

To evaluate the prognostic role of other molecular alterations (e.g. *MET*, *EGFR* or *HER2* amplification) for *sensitivity* to afatinib plus cetuximab or afatinib alone, for each potential marker, a chi-squared or Fisher's exact test at the 5% level will be used to compare response rates between patients with amplification versus patients without amplification.. The following table details the power to detect a 30% difference in response rates using a 1-sided 0.05 level test across a range of possible marker prevalence.

Marker prevalence	Power
5%	46%
10%	76%
15%	90%
20%	95%

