Preliminary Data: To identify new mechanisms of resistance and understand the genomic complexity and evolution of *EGFR* mutant tumors, we have performed whole exome sequencing (WES) of 22 pre- and post-treatment specimens from patients with *EGFR* mutant lung cancer. The mean number of treatment-acquired mutations in these samples was 26 (range 0-94). Non-synonymous mutations in cancer genes (defined by the Cancer Gene Census) were enriched in resistant tumors compared to pre-treatment specimens. Mutations in cancer genes were more frequently retained in the post-treatment specimens compared to non-cancer genes suggesting that the former are undergoing selection in the presence of drugs. These preliminary studies highlight the feasibility of obtaining, performing and analyzing WES from lung cancers before and at resistance to EGFR TKIs.

Research Design and Methods: The Nimblegen/Roche solution-capture exome array will be used for exome capture followed by sequencing on the Illumina HiSeq platform. This technology is routinely used on FFPE material at the Yale Center for Genome Analysis. This analysis will utilize FFPE and frozen tissue.

Statistical Design: The evaluation of each mutated gene's prognostic value will be analyzed in a similar fashion as described in section b above. Since the number of genes investigated may be large, an adjustment for multiple comparisons (e.g. Bonferroni) will be employed.

To assess whether mutations in will be detected more frequently in tumors with acquired resistance to afatinib plus cetuximab compared to afatinib alone, exact 95% confidence intervals will be constructed for the proportion of mutations observed on each arm. Assuming 50 patients per arm, the true proportion of patients with a specific mutation can be estimated to within at least 14%.

d. **EGFR Immunohistochemistry (INTEGRATED)**

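### Section 18.1c relies on a multiplicity adjustment of log-rank p-values for every mutated gene, but for genes carried by very few patients the adjustment does not control false findings

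*Combined protocol and SAP*

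**What the plan says.** Section 18.1c (whole exome sequencing), Statistical Design, does not write out its own prognostic test. It refers back: each mutated gene's "prognostic value will be analyzed in a similar fashion as described in section b above". It then adds: "Since the number of genes investigated may be large, an adjustment for multiple comparisons (e.g. Bonferroni) will be employed". The number of genes is not given.

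The method it borrows is in Section 18.1b, Statistical Design, item 1. For survival outcomes, "a logrank test at the 5% level will be used to compare OS and PFS between patients with amplification versus patients without amplification". For response, "a chi-squared or Fisher's exact test at the 5% level will be used to compare response rates". An exact option is therefore named for response but not for PFS or OS. The power table in 18.1b is calculated "using a 2-sided 0.10 level logrank test across a range of possible marker prevalence", and its lowest prevalence is 5%. For rarer amplifications (HER2 about 1%, MET about 3% at baseline) 18.1b warns that power will be low, and gives no other caution.

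Neither section sets a minimum number of mutated patients for a gene to be tested.

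**The concern.** A Bonferroni-type adjustment works only if each p-value is accurate at the very small level to which it is compared. A log-rank test with a normal reference distribution is accurate there when both groups are reasonably large. Exome data also contain genes mutated in only one or two patients, and 18.1c sends these through the same test. If such a carrier happens to progress or die early, the statistic can be huge by chance alone.

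The adjustment is the only protection against false findings that 18.1c states, and one aim of the section is to find new genes linked to response and resistance. If the adjustment fails for rare genes, chance mutations in a few early progressors can be labelled significant after adjustment. That label misleads more than an openly unadjusted list would.

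**Working it through.** The plan gives no error rate, gene count or threshold for this analysis, so there is no figure of its own to reproduce.

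**Inputs**
- Assayed patients: Section 11.2c reduces the trial to 212, and Section 18.1a assumes about 20% without a baseline result. 0.8 × 212 = 169.6, so about 170. Section 18.1a itself still uses 460, so that is shown too.
- PFS events: 134 of 212 (63%) in the revised design (Section 11.2c); 446 of 576 (77%) in the original design (Section 11.2b).
- PFS medians 13.7 and 10.8 months, 56% exon 19 (Section 11.1); arm hazard ratio 0.57 (Section 11.2c); follow-up capped at 3 years (Section 7.8).
- Gene family: not stated. Assumed range 500 to 20,000.
- Sidedness: 18.1b states a 5% level but powers at two-sided 0.10, so both one-sided and two-sided 5% family levels are shown.

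**Step 1. One carrier, by formula.** If the only carrier has an event when the pooled cumulative hazard is H, observed minus expected is 1 − H and the variance is about H, so z ≈ (1 − H)/√H.
- The one-sided 20,000-gene cut-off is 0.05/20,000 = 0.0000025, or z = 4.565.
- Setting (1 − H)/√H = 4.565 gives √H = (−4.565 + √(4.565² + 4))/2 = 0.2095, so H = 0.0439.
- The chance of an event that early is 1 − exp(−0.0439) = 4.3%. The nominal chance is 0.00025%.

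**Step 2. The extreme case.** With 170 at risk, the first patient to fail contributes observed minus expected of 169/170 and variance (1/170)(169/170), so z = √169 = 13.0. If that patient has a mutated gene that nobody else has, the gene passes every cut-off considered here. Without censoring, exact enumeration for 170 patients shows that a sole carrier passes the two-sided 500-gene cut-off if among the first 9 to fail (9/170 = 5.3%), and the two-sided 20,000-gene cut-off if among the first 6 (6/170 = 3.5%).

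**Step 3. Simulation with no gene effect.** The one-sided column uses the medians, hazard ratio and cap above, and its ranges show the spread over repeated runs. The two-sided columns use 63% events and 40,000 replicates per row.

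| Carriers of 170 | 20,000 genes, one-sided (nominal 0.00025%) | 20,000 genes, two-sided (nominal 0.00025%) | 500 genes, two-sided (nominal 0.01%) |
|---|---|---|---|
| 1 | 4.1% | 3.5% | 5.1% |
| 2 | 1.05–1.1% | 1.0% | 2.0% |
| 3 | 0.44–0.49% | 0.41% | 0.9% |
| 5 | 0.14–0.15% | 0.10% | 0.39% |
| 9 | not run | 0.025% | 0.16% |
| 17 | 0.009–0.012% | 0.005% | 0.06% |
| 85 | not run | 0% | 0.0075% |

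For one carrier the excess is 4.1/0.00025, about 16,000-fold, for 20,000 genes, and 5.1/0.01, about 500-fold, for 500 genes. With 460 patients, 77% events and 20,000 genes two-sided, the rates are 4.0% and 1.1% for one and two carriers. All rejections at one and two carriers were in the harmful direction. With 85 of 170 carriers, as for TP53, there is no material inflation.

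**Step 4. Ties.** The simulation uses continuous event times. Progression is found mainly at 8-week scans, so I repeated it with PFS dates spread over one to two weeks around each scan, and the rates barely changed. Only if every progression fell exactly on a common scan day would the one-carrier PFS rate drop substantially, and it would still be far above nominal. Deaths are not tied to scans.

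**The case against.** **The plan does not say large-sample.** It names a log-rank test, says that genes are handled similarly to 18.1b, and offers Bonferroni only as an example. This stands as a matter of wording. But a log-rank test named without qualification is ordinarily read as the one with a normal reference, and 18.1b names an exact alternative only for response. Replacing Bonferroni with Holm or a false-discovery-rate method would not help, because the p-values fed in are already wrong.

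**Analysts would drop the rarest genes.** Perhaps, but the text covers each mutated gene, and a filter chosen after seeing the data is not prespecified. Nor is a filter enough: at 17 of 170 carriers the one-sided rate is still about 40 times nominal.

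**A count of false genes.** A reader might infer that well over 100 false genes would be reported. Assuming 26 mutated genes per tumour spread evenly over 20,000 genes, the mean number of carriers per gene is 170 × 26/20,000 = 0.221. That gives about 3,540 one-carrier genes × 4.1% = 145, plus about 390 two-carrier genes × 1.1% = 4. The documents do not support this as a forecast. The 26 in Section 18.1c is a mean of treatment-acquired mutations, not of baseline mutated genes. The 20,000 is an assumption, and mutations are not evenly spread. Nearly all of these genes have one carrier, and they would cluster in a handful of early progressors, a pattern that is easy to recognise. With one private gene per patient (170 genes, two-sided) the expected number is about 10. That the adjustment fails does not depend on these counts; how many genes are affected does.

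**Reach.** The named TP53 hypothesis involves a common gene. The comparison of acquired mutations by arm uses exact confidence intervals. The primary PFS comparison and the stopping rules do not use these tests. All of this stands.

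**Conclusion.** The concern holds for the untargeted gene search on PFS and OS in Section 18.1c. Followed as written, with the usual normal reference, the stated test plus adjustment does not control false findings among genes with few carriers. With about 170 assayed patients, one-carrier genes pass about 4% of the time and two-carrier genes about 1%, against a nominal 0.00025% (20,000 genes, one-sided). For 500 genes, two-sided, the rates are about 5% and 2% against 0.01%. The conclusion is the same with 460 patients.

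It rests on three assumptions: a normal reference for the log-rank test, 80% assay yield at 212 patients, and a gene family between 500 and 20,000. The number of false genes cannot be forecast, because the documents give neither the gene count nor the baseline mutations per tumour. A reader might also infer that the exome results as a whole, or the trial's main conclusions, are unsafe. The documents do not support that: common genes, response tested by Fisher's exact test, the exact intervals by arm and the primary PFS analysis are untouched.

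**What to change.** In Section 18.1c, state that each gene's PFS and OS p-value comes from a permutation log-rank test, with mutation status permuted within treatment arm and EGFR mutation type. Apply the multiplicity adjustment to those p-values, or use the permutation max-statistic (Westfall-Young). Define the gene family and the sidedness in the same place.

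With four strata, equal arms and 56% exon 19, the strata hold about 85 × 0.56 = 48 and 85 × 0.44 = 37 patients. A one-carrier gene's p-value then cannot fall below about 1/48 to 1/37 (0.021 to 0.027), so it cannot be flagged after adjustment.

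Two practical points follow. If p-values are adjusted one by one, the number of permutations must resolve the cut-off: 0.0000025 needs at least 1/0.0000025 = 400,000. If the max-statistic is used, build it on the permutation p-values or leave out the rarest genes; otherwise their extreme z values (up to 13) would set the cut-off for every gene.

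A small prespecified minimum carrier count, with rarer genes listed descriptively, is optional. Permutation is valid without it.

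The cost is two or three sentences and computing time. The downside is that the rarest genes cannot reach significance, but the test they have now is not valid for them.

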18.2 Intake Calendar - Afatinib

SWOG Patient ID _____	Patient Initials (L, F, M) _____	SWOG Study # S1403				
Institution/Affiliate _____	Physician _____					
Treatment _____	Start Date: _____	Start Day (Circle One): Sun M Tu W Th Fr Sat				
Instructions for the participant:						

Afatinib is a tablet you take once a day. This is a 28 day cycle calendar on which you are to put the date in the small box on the calendar and record the time you take your afatinib tablet (or the reason a dose was not taken) in the larger part of the box. Take the tablet as directed by the study doctor. Afatinib should be taken once a day on an empty stomach (i.e. one hour before or two hours after a meal). If you miss a tablet, take it as soon as you remember EXCEPT if your next scheduled dose is in less than 12 hours. In that case, just take the next tablet at your regular time. Tell your doctor about the medicine you take including prescription medicines, over-the-counter medicines, vitamins, and herbal supplements. If you develop any side effects from the afatinib tablet, mark this on the calendar on the day you note the effect. Be sure you have enough calendars to last until your next appointment. Bring your calendars and your pill container with leftover tablets with you each time you have an appointment.
						
If you have questions contact: _____ Telephone: _____						
Your next appointment is: _____						
Special instructions:						
Month: _____ Year: _____						
Sunday	Monday	Tuesday	Wednesday	Thursday	Friday	Saturday

Patient Signature: _____ Date of CRA Review: _____

18.3 SWOG **S1403** Pathology Review Form

SWOG **S1403** Pathology Review Form
SWOG Solid Tumor Biorepository

SWOG ID # _____
Protocol of Interest: **S1403**

Patient Initials: _____(L, FM)

Pathology Diagnosis: _____

Please indicate time point:

Baseline Repeat biopsy after progression

Preliminary Data Specimen Submission:

Resected Tissue Core Biopsy Fine Needle Aspiration (FNA)
Effusion

Specimen Type Submitted:

Block – Surgical Pathology Number* _____

Slides – Surgical Pathology Number* _____

* This is **not** the number given to the specimen from the Specimen Tracking System.

Specimen Review

1) Please confirm that a minimum of 12 unstained slides are available:

Note: Submission of 1-2 paraffin-embedded blocks is strongly encouraged. However, if blocks are unavailable, 15-20 unstained slides are acceptable alternatives (12 slides is the absolute minimum).

Adequate (≥ 12 slides) Inadequate (< 12 slides)

2) Tumor Cells Available (PLEASE CHECK ONLY ONE):

Adequate (≥ 100 cells) Inadequate (< 100 cells)

Signature of Interpreting Pathologist

Date

NOTE: A copy of this form is to be submitted along with the pathology report to the SWOG Solid Tumor Specimen Repository as outlined in [Section 15.4.- 15.6](#), This form must also be uploaded via the Source Documentation: Follow-up in RAVE

Comments:

18.4 Jackson Laboratory Sample Submission Form

REQUISITION FORM: PATIENT DERIVED XENOGRAFT

Protocol Name: RANDOMIZED PHASE II TRIAL OF AFATINIB PLUS CETUXIMAB VERSUS AFATINIB ALONE IN TREATMENT-NAÏVE PATIENTS WITH ADVANCED, EGFR MUTATION POSITIVE NON-SMALL CELL LUNG CANCER (NSCLC)

Protocol Number: **S1403**

Submitting Institution:

PATIENT INFORMATION

SWOG Patient ID # _____
JAX PDX # _____ (assigned by JAX)

SPECIMEN INFORMATION

Date collected: _____
Date Shipped: _____ (If different from date collected)

SPECIMEN TYPE

Biopsy – Estimate of amount of tissue sent: # _____ Cores, _____ mm (L) x _____ mm (D)
 Surgical resection – Estimate amount of tissue sent: # _____ Cores, _____ mm (L) x _____ mm (D)
 Pleural Effusion – Estimate volume of fluid sent: _____ ml

Is the submitted specimen free of necrotic tissue? Yes No

Is the submitted specimen free of excess blood? Yes No

Comments: _____

Prior sample on this patient submitted for PDX? Yes No

If yes, Prior patient study ID # _____

SITE PRINCIPAL INVESTIGATOR CONTACT INFORMATION

Name: _____

Primary Phone: _____

Email: _____

AUTHORIZATION

I certify that this specimen was collected with the patient's informed consent

X

Date

See page 2 for specimen collection and shipping instructions

PDX SPECIMEN COLLECTION AND SHIPPING INSTRUCTIONS

Contact Pathology prior to collection to coordinate and expedite sample processing.

The surgeon should obtain the maximum amount of tumor that is prudent at the time of biopsy or resection.

The specimen should be collected following Institutions Universal precautions SOPs for maintain tissue integrity and delivered immediately to Pathology. Please remind all personnel that are involved in processing the sample that it will be implanted in severely immune deficient mice, which is why we request that extra care be taken in sample collection to minimize the risk of transferring human bacteria to the mice.

Collection process for biopsy and surgical material

Materials needed:

Provided by JAX	Provided by the site
15ml tube containing transport media	Sterile forceps for transferring specimen to the tube containing transport media
50ml transport tube (no media)	Parafilm
Biohazard Specimen Bag 6" x 9"	Clean Gloves
Gelpacks	Alcohol or similar to clean gloves before handling the tissue
Insulated shipping container	
Prepaid shipping labels	

Using sterile forceps, transfer the tumor material collected at the time of biopsy or surgical resection to the 15 ml tube containing the transport media that is provided in the sample shipping kit. This transfer should occur as soon as possible, preferably within 30 minutes of tumor removal. The submitted tumor material should be free of necrotic or excessively bloody tissue.

Seal cap tightly with Parafilm and place in the larger 50 ml tube. This tube is provided for extra protection in shipping. Place the tube at 4 degrees until it is packed for shipping. This specimen for PDX development should NEVER be frozen.

Collection process for Pleural Effusions

Pleural fluid is collected and sent to cytology. Cytology staff will centrifuge ~40 - 50ml of the fluid. The remaining cells at the bottom of the tube (button) are then mixed with Transport Media and sent to JAX.

Packing and Shipping Instructions

JAX will provide shipping containers and labels. The sample will normally be shipped by Fed Ex unless it is collected too late in the day, in which case we will order a courier and have an electronic label sent to you. Contact [contact] as soon as the biopsy is scheduled to plan for the most expeditious shipping method.

Place the 50 ml tube containing the smaller tube with the tumor sample and transport media into the biohazard bag and seal (the biohazard bag is self-sealing). Place the bag in the insulated shipping container along with the gel packs that have been cooled to 4 °C (0°C~6 °C); the gel packs should NEVER be frozen.

Ship the package according the previously agreed on method. Notify [contact] that the sample has been picked up. JAX will notify the study coordinator when the sample is received at its site.

V.2 103015

18.5 New York Heart Association Criteria

Class	Cardiac Symptoms	Need for Limitations	Physical Ability Additional Rest*	To Work**
I	None	None	None	Full Time
II	Only moderate	Slight or occasional	Usually only slight	Usually full time
III	Defined, with less than ordinary activity	Marked	Usually moderate	Usually part time
IV	May be present even at rest, & any activity increases discomfort	Extreme	Marked	Unable to work

* To control or relieve symptoms, as determined by the patient, rather than as advised by the physician.

** At accustomed occupation or usual tasks.
